****VUMC ONLY:** Due to the unprecedeted situation surrounding the global COVID-19 pandemic, we will, via email, ask currently-enrolled families (only at the VUMC site) from Cohort 4 and 5 (and all future subjects) to complete the following three questionnaires, which relate to stress and coping associated with COVID-19, via REDCap online survey or, if they choose, using physical copies of the questionnaires that we would mail to them:

VUMC ONLY: 1) Compas Responses to Stress Questionnaire (RSQ; Compas, 2020) - COVID-19 Child Self-Report: The RSQ can be filled out by children and adolescents regarding their own personal coping and involuntary stress responses in regards to how they respond to stress related to COVID-19.

VUMC ONLY: 2) Compas Responses to Stress Questionnaire (RSQ; Compas, 2020) - COVID-19 Adult Self-Report: The RSQ can be filled out by parents regarding their own personal coping and involuntary stress responses in regards to how they respond to stress related to COVID-19.

VUMC ONLY: 3) Compas Responses to Stress Questionnaire (RSQ; Compas, 2020) - COVID-19 Parent Report on Child: The RSQ can be filled out by parents regarding their child's coping and involuntary stress responses in regards to how their child responds to stress related to COVID-19.

ASSESSMENT VISIT

SETUP & CONSENTING

- Arrive at the assessment facilities 30 minutes prior to family arrival time.
- Gather appropriate testing materials out of cabinets (ADOS, NEPSY, WASI)
- When the family arrives bring them into a private family room and begin consenting. (15 minutes)
 - Ensure that 2 consent & 2 assent forms are signed by the family and research staff (1 copy for research team & 1 for family)
 - Take the **child's photo** (after parent or guardian has signed Video/Photo Release). Explain that picture will be used during counselor/peer matching.
 - Explain **NDAR** (National Database for Autism Research), and also explain GUID and need for **child's city of birth** in creating unique identifier (see page 14).
- Leave the parent in the family room where they'll wait until the assessment is done with child
 - Retrieve any filled surveys that will be scored later, make sure to check that all files have been answered entirely
- Consenting for Peer Control Group:

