Investigating Social Competence in Youth with Autism: A Multisite
RCT

Statistical Analysis Plan (SAP)

NCT03368001

Document Date: November 1, 2017

Document Source: Analytic Plan from MH114906

3.C.12. ANALYTIC PLAN: Aims and Hypotheses (Hyp)

Handling missing data, Full information maximum likelihood (FIML) estimation methods will be used.

Specific Aim 1: Show Efficacy of SENSE via Target Engagement of Memory for Faces

Hyp 1.1: Youth in the EXP group will demonstrate significantly faster growth in memory for faces (MFD and IMF) than youth in the ACC group. EXP youth will also have higher levels of memory for faces at follow-up.

Hyp 2.1: Youth in the EXP group will demonstrate significantly faster growth in social behavior (SRS and CASS) than youth in the ACC group. EXP youth will also have higher levels of prosocial behavior at follow-up.

Statistical Analysis: To address the above-mentioned hypothesis, we will use a 2-level multilevel growth model with treatment (EXP vs. ACC) predicting random intercepts and random linear slopes. The levels are (1) time of testing in months from study entry and (2) participant. Time will be centered at follow-up to enable interpreting the intercept as an end-point estimate. We will test EXP vs. ACC differences on means of the linear slope of time in order to test for differential change over time. We will also test EXP vs. ACC differences in follow-up-centered intercepts. A linear model is a reasonable model of social growth for such a short period (i.e., three months) with people who have a social impairment. The random intercept and slope accommodate dependency of time (pre, post, follow-up) within participant. Dependency of participants within cohort will be corrected for using design-robust standard errors (following procedures in Sterba¹²⁶). Site effects are not anticipated but will be examined by including 2 dummy covariates for site as predictors of intercepts and slopes; if not significant, these covariates will be removed. This model will be run in Mplus¹²⁷ general multilevel and structural equation modeling software capable of fitting both the univariate multilevel models for Specific Aim 1 and the multivariate multilevel models for Specific Aim 2, below.

Specific Aim 2: Linking Degree of Target Engagement and Mechanism-Based Functional Outcomes

Hyp 2.2. Growth in memory for faces (NEPSY, ERP) will mediate the effect of treatment on growth in social behavior (SRS, CASS).

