Statistical Analysis: To address Hyp 2.2, we will use a multivariate multilevel growth model (involving a linear growth model for memory and another linear growth model for social behavior). We will specify a mediation pathway at the participant-level from treatment (x) to the slope of memory for faces (m) to the slope of social behavior (y). The indirect effect will be tested using the 95% confidence interval around the product of the unstandardized coefficients for the (x→m) and (m→y) paths of the multilevel mediation model following procedures of Lachowicz, Sterba, and Preacher¹²⁸. The confidence interval will be estimated using the Monte-Carlo procedure described in Preacher and Selig,¹²⁹. Exclusion of zero will be interpreted as a significant indirect effect.

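### The Hyp 2.2 mediation model has no term for the pandemic period, so a shift in both slopes could bias the memory-to-social-behavior path; the size is unknown and may be small

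*Protocol*

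**What the plan says.** **Exposure.** Under Survey Kit, in the part for the pre-test visit, the protocol says that the Vanderbilt (VUMC) site will "ask currently-enrolled families (only at the VUMC site) from Cohort 4 and 5 (and all future subjects) to complete the following three questionnaires", all about stress and coping in the pandemic. The documents do not give the number of cohorts or their dates. They do not say which visits of Cohorts 4 and 5 fell in the pandemic, or what happened at the other sites.

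**Model.** The SAP carries the line "Document Date: November 1, 2017". For Hyp 2.2 (Specific Aim 2, Statistical Analysis) it specifies a "mediation pathway at the participant-level from treatment (x) to the slope of memory for faces (m) to the slope of social behavior (y"). The test uses a Monte Carlo "95% confidence interval around the product of the unstandardized coefficients" for the two paths, and "Exclusion of zero will be interpreted as a significant indirect effect". No covariate is listed.

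**Cohort, site and time.** These are described in the preceding Statistical Analysis paragraph, for Hyp 1.1 and 2.1:
- Cohort: "Dependency of participants within cohort will be corrected for using design-robust standard errors".
- Site: "including 2 dummy covariates for site as predictors of intercepts and slopes; if not significant, these covariates will be removed".
- Time is counted in months from each participant's entry, so calendar date does not enter.

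The Hyp 2.2 paragraph does not repeat the cohort or site provisions.

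**The concern.** The indirect effect is the product of two paths. The first, treatment to memory slope (path a), is randomized. The second, memory slope to social-behavior slope given treatment (path b), is observational. Anything that moves both slopes for the same participants is a common cause of mediator and outcome, and it makes them correlate with no causal link.

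A pandemic that begins partway through a cohort-based trial is a candidate for such a cause. Cohort-robust standard errors widen or narrow the interval but leave the point estimate of path b where it is.

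Hyp 2.2 is the trial's mechanism claim: that engaging the target, memory for faces, carries through to social behavior. The decision rule is simply whether the interval excludes zero. With a real treatment effect on memory, a period-induced path b can therefore be reported as mediation. If the period moved the two slopes in opposite directions, a true effect could be hidden.

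**Working it through.** **1. Inputs from the documents.** N = 216, expected treatment effect d of at least .5, expected standardized indirect effect of at least .23, and smallest detectable indirect effect .056 (all SAP, power section); a 95% Monte Carlo interval (SAP, Specific Aim 2).

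**2. Assumptions, not in the documents.** Share of participants in affected cohorts p; shifts g in the memory slope and h in the social slope, in residual slope SDs; slope reliability; number of cohorts; arms balanced within cohort; true path b = 0.

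**3. The plan's own figure.** The .056 can be neither confirmed nor refuted, because power depends on how the product splits between the paths. Simulated power at N = 216 is 87% for .237 × .237, 83% for .20 × .28 and 49% for .40 × .14. It serves here only as a yardstick.

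**4. Bias in path b.** Omitting the period gives

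estimated b → b + g·h·p(1−p) / [s² + g²·p(1−p)],

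where s² is the residual variance of the memory slope. With b = 0, g = h and p = .4, p(1−p) = .24:

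| Shift (SD) | Error-free slopes (s² = 1) | Reliability .5 (s² = 2) |
|---|---|---|
| .5 | .060/1.060 = .057 | .060/2.060 = .029 |
| .8 | .1536/1.1536 = .133 | .1536/2.1536 = .071 |
| 1.0 | .240/1.240 = .194 | .240/2.240 = .107 |

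At a shift of .3 with error-free slopes the bias is .0216/1.0216 = .021.

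**5. Size of the false indirect effect.** With 1:1 arms the treatment indicator has SD .5, so d = .5 gives a standardized path a of about .5 × .5 = .25. At a 1.0 SD shift with error-free slopes the false product is about .25 × .194 = .048. That is close to .056 and well below .23.

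**6. How often mediation is falsely declared.** Simulated with d = .5, N = 216, 15 assumed cohorts and cohort-robust standard errors. Ranges cover separate runs.

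| Setting | .5 SD | .8 SD | 1.0 SD |
|---|---|---|---|
| Reliability .5, 40% of cohorts affected | 5-7% | 14-15% | 21-24% |
| Reliability .5, 20% affected | 7% | 9% | 14% |
| Reliability .3, 40% affected | 4% | 6% | 9% |
| Reliability .3, 20% affected | about 5% | about 5% | about 5% |
| Error-free, 40% affected | 16-17% | 48-51% | 76-80% |
| Error-free, 20% affected | 11% | 25% | 39% |

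With error-free slopes and no shift at all the rate is already 7-8%, so not every excess over 5% is due to the period. Adding a period term brings every case back to roughly 2-9%.

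**7. Conditions needed.** A second layout (12 cohorts of 18, half affected, error-free slopes) isolates them, using ordinary standard errors:
- If only one slope shifts by .8 SD, the rate is 4.9%.
- If the shifts are .8 SD in opposite directions, false mediation of the opposite sign appears in 51%.
- With d = .2 the rate is 3% at .5 SD and 18% at 1.0 SD.
- With d = 0 the rate is at most 2.4% (6.8% with cohort-robust errors), and the mean product is about zero.
- With d = .5, switching to cohort-robust errors leaves the mean product unchanged. It is .100 at a 1.0 SD shift either way, and the rejection rate is 77% with ordinary and 81% with robust errors.

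**The case against.** **No visit is shown to have taken place in the pandemic.** A reader might infer from the questionnaire paragraph that a large part of the trial's data was collected under pandemic conditions, or that all sites were affected. The text supports less: one site, two named cohorts enrolled at the time, and later subjects anticipated. Some of those families may already have finished their visits. This stands, and the share affected has to be treated as unknown.

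**A change in level is not a change in slope.** A cohort seen wholly within the pandemic may differ only in its intercept, which the growth model absorbs. The clearest disturbance of slopes is in participants whose visits straddle the onset. This also stands. It is a reason to separate straddlers in the indicator, not to leave period out.

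**The large rates need error-free slopes.** They also need shifts of .8 to 1.0 SD in both slopes. Slopes here come from three waves, so the reduced-reliability rows are the more realistic guide, and at a .5 SD shift they are close to the no-shift rate. This stands as to size. The planned model estimates slopes as random effects, so none of the rows reproduces it exactly. The direction of the bias does not depend on this.

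**The SAP predates the pandemic.** A reader might call the missing term a flaw in the original design. It is a missing update.

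**Aim 1.** A reader might extend the point to the treatment comparisons in Hyp 1.1 and 2.1. Randomization protects those contrasts, and they do not need this change.

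**Conclusion.** The concern holds as a gap in the Hyp 2.2 model. The protocol records that the pandemic arose while the trial had participants enrolled at one site. The mediation path between slopes is not randomized, and nothing in the SAP adjusts it for calendar period.

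A false result requires three things together: a treatment effect on memory for faces, a period shift in both slopes, and shifts that are large relative to slope SD. Under the more realistic setting (reliability .5, 40% of cohorts affected), false mediation rises to about 14-15% at .8 SD and 21-24% at 1.0 SD, and stays at 5-7% at .5 SD. Error-free slopes give about 16%, 50% and 78% at the three shifts, which is better read as an upper case. At .3 SD or less, or at reliability near .3, the rates are near those with no shift.

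The documents give no evidence on the share affected, the size of any shift or the reliability. They therefore do not support a statement that the Hyp 2.2 result is, or will be, spurious. What they support is an inexpensive improvement to the model.

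**What to change.** Amend the SAP for Hyp 2.2 as follows.

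1. Derive a pandemic-period indicator from visit dates with three categories: all visits before onset, visits straddling onset, and all visits after. State the onset date used.
2. Let it predict the intercepts and slopes of both memory for faces and social behavior. Keep it in the model regardless of significance, unlike the site dummies.
3. Report Hyp 2.2 in participants whose visits all preceded the onset, as a sensitivity analysis.
4. Report how many participants at each site fall in each category, so that the reader can judge exposure.

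The Aim 1 model can stay as it is.

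The cost is SAP wording and one or two covariates from visit dates. If the period had no effect, the price is a few degrees of freedom and a slight loss of precision. The pre-pandemic subset will be smaller and its interval wider, so it should be read for consistency and not as a second test. If the Hyp 2.2 result has already been seen, label the change as post hoc.

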***Follow-Up forms sent to both Experimental and Control groups approximately 8 weeks after post-visits.**

FOLLOW- UP ERP

- Protocol for ERP does not change in follow-up visit.
- ERP may come before Assessment during follow-up

FOLLOW- UP CASS

- Utilize research helpers unknown to participant (not the same research helpers as in the pre and post- CASS)

SENSE THEATRE/TACKLING TEENAGE TRAINING INTERVENTION PREPARATION

GROUP ASSIGNMENT

- Once randomization into SENSE Theatre or TTT is complete and participants have been assigned to groups, send letters to families informing them of what group they are assigned.
- Send out RedCap survey which collects information regarding Medication (see if there have been any changes), food allergies, behavioral information, t-shirt size.
- Add participant and research helper contacts to a designated lab cell phone

PEERS/COUNSELORS

- **Application:** Interested peers and counselors will complete an application
- **Decisions:** Lead site investigator, and theatre director will narrow down who is to be interviewed for a peer and counselor position.
- **Background checks:** all adults participating in the intervention (18 years +) must have an existing background check with Vanderbilt or go through the process of getting one.
- **Protection of Minors Training:** Make sure all counselors and peers are compliant with the site's requirements for protections of minors training. Contact site IRB for "Research Involving Minors" for more information pertinent to site requirements.
- **Consent and Video Release Forms:** sent to peers/counselors participating in intervention.
- **Intervention Information:** Send training schedule, location map, and first days schedule (via email), and an email reminder 1 week before training begins.

TRAINING

SPEAKERS

- Site PI will be responsible for contacting and choosing speakers.
- Coordinate who will be presenting when, 6 weeks before intervention begins.
 - Research Assistant/Coordinator—"Introduction to Autism"
 - Confidentiality & Code of Conduct, SENSE Theatre Manual, SENSE Lab & Theatre, Behavioral Strategies.
- Copies of past presentations can be provided to any sites by the SENSE Research Coordinator.

BINDERS

- Binder Materials:
 - Binder Covers (Color)
 - Binder spine labels (color)

- Divider Tab Labels
- Presentations (Black and White)
- Schedule
- Music/Lyrics (SENSE Theatre Intervention only)
- Name Tags
- Pre/Post Test
- SENSE Theatre Manual (Black and White)
- Script (Black and White) (SENSE Theatre Intervention only)
- The lead site investigator, theatre director, research assistant/coordinator, and nurse(s) should be provided a sheet that details participant contact information, allergies, and medications, along with a picture for identification purposes.

FOOD

- Create catering order 3-5 days in advance
 - A light breakfast, coffee and bagels
 - Lunch based on preference (sandwiches, pizza, salads, etc.)

ROOM

- Reserve Room 2-4 weeks in advance.
- Coordinate room reservations with administration. Classrooms with projectors and whiteboard are best, conference rooms if the group is small.

INTERVENTION

Intervention Packets: before Intervention begins the following should be sent to participants 1 month before it begins.

- Letter to Parents
- Schedule with important dates
- Release Forms
- First Day Schedule
- Intervention checklist

DAILY TASKS:

- **Daily Schedule:** coordinate with lead site investigator and theatre/training director after each day of intervention program to determine schedule for next session.
- **Daily Email:** [name] will send first and last email to parents, peers, and counselors.
 - Each day, you will give a brief review of the day; give any reminders, updates, etc. Also attach schedule for next session.
- Prepare Snacks/Waters for participants/counselors/peers.
- Bring extra copies of schedule for Dry Erase Board and any participants that need a hard copy.
- Check attendance, call families who may be running late, etc.

ONLINE VIDEOS

[figure not shown]
- Contact site information technology regarding uploading peer modeling videos to a password protected website for families to access at home.

ORDERING

- Snacks
 - Lay's Chips, Gold Fish, Fruit Snacks, Water, Granola Bars
- T-Shirts:
 - Lead site investigator and site graphics design will coordinate on t-shirt design and ordering.
- Binders:
 - 1 ½" for peers/counselors
 - 1/2" for participants
 - Dividers for peer and participant binders
- Any Props/Equipment used for the production
 - Past examples include stress balls, Bradfield Lighting, etc.
 - Costumes
 - Usually provided by theatre team and participants
 - Theatre director will set up a time for costumes to be coordinated
 - Prepare a document that states:
 - What participant is wearing from site
 - What items they need to bring from home to complete costume.

CONSTANT CONTACT (PERFOMANCE INVITES)


- In order to submit data to NDAR each participant you're submitting data for must have a GUID (Global Unique Identifier)
- To create a GUID, one must have subject Legal Name at Birth, Date of Birth, Sex, and City/Municipality of Birth.
- Create a GUID by first putting in identifying information into GUID template found here.

- GUIDs are created by going to the **GUID Tool** which can be found on the [NDAR home page](#) under **resources**. Instead of submitting the forms for each individual separately use “Get GUIDs for Multiple Subjects” under the “Functions” tab.

- Then you will upload your GUID .csv file:

	A	B	C	D	E	F	G	H	I	J	K	L
1	ID	FIRSTNAME	MIDDLENAME	LASTNAME	MOB	DOB	YOB	COB	SEX	SUBJECTHASMIDDLENAME	USEEXISTINGGUID	
2	401	John		Doe		1	1	1999	Nashville	M	NO	YES
3												
4												
5												

[figure not shown]
ID=Study ID, so for SENSE Theatre it would be the numbers after ST.

Middle name is not required for a GUID, if you have subject middle name, then you would enter “YES” under the column “SUBJECTHASMIDDLENAME”

- Upload your excel .csv file, and then create GUIDs. GUIDs will automatically be saved in the folder in which you saved the GUID .CSV file [here](#). You can also **copy and paste the output into a spreadsheet**.

SUBMITTING DATA TO NDAR: DATA VALIDATION TOOL

- Data validation tool can be found on NDAR homepage under Resources as well.
- Choose data you wish to upload and validate.

- 1: Load files
- 2: Validate files
- 3: Check Errors/Warnings
- 4: Validate again
- 5: Repeat steps 2-4 if needed.
- Build Submission Package once all files are found to be valid.
- Upload Package
- Check NDAR site for submitted data.

NDAR CONTACTS

Name	Email	Phone
NDAR Help**	[contact]	[contact]
[name]	[contact]	[contact]

IMPORTANT NOTES ABOUT NDAR

- For every NDAR submission, NDAR expects the submission to be cumulative, so submit everything you have ever submitted to NDAR for that data set each time you submit.
- Also, even if there is nothing new with your data at the submission date, still submit data.
- Sometimes you will notice during Validation, errors arise that seem to be related to the original template or data dictionary → email or call NDAR help with these issue. Sometimes corrections to templates must be made on their end.
- Private vs. Public: Be sure to check the NDAR collection page.

- Check “Share” dates for collection.
- Demographic-early release date
- Dependent measures: released upon publication/completion of grant.
- Useful NDAR information [here](#)

MISCELLANEOUS

- VUMC SITE ONLY: iMotions Software Analysis
 - These analyses use videos of participants’ faces and are done using iMotions, a well-established computer program that measures how the face moves and computes deidentified values for various emotional facial expressions. This is accomplished statistically, comparing the actual appearance of the face and the configuration of the features numerically with normative databases provided by facial expression engines. The program only identifies expression of emotion; it does not use facial landmarks or any other means to identify who is in the video nor does it store recordings to improve its internal database and algorithms.
 - After initial upload to the iMotions program, videos will be deleted from the program, at which point de-identified numerical data will be used for the remainder of analyses.

Investigating Social Competence in Youth with Autism: A Multisite
RCT

Statistical Analysis Plan (SAP)

NCT03368001

Document Date: November 1, 2017

Document Source: Analytic Plan from MH114906

3.C.12. ANALYTIC PLAN: Aims and Hypotheses (Hyp)

Handling missing data, Full information maximum likelihood (FIML) estimation methods will be used.

Specific Aim 1: Show Efficacy of SENSE via Target Engagement of Memory for Faces

Hyp 1.1: Youth in the EXP group will demonstrate significantly faster growth in memory for faces (MFD and IMF) than youth in the ACC group. EXP youth will also have higher levels of memory for faces at follow-up.

Hyp 2.1: Youth in the EXP group will demonstrate significantly faster growth in social behavior (SRS and CASS) than youth in the ACC group. EXP youth will also have higher levels of prosocial behavior at follow-up.

Statistical Analysis: To address the above-mentioned hypothesis, we will use a 2-level multilevel growth model with treatment (EXP vs. ACC) predicting random intercepts and random linear slopes. The levels are (1) time of testing in months from study entry and (2) participant. Time will be centered at follow-up to enable interpreting the intercept as an end-point estimate. We will test EXP vs. ACC differences on means of the linear slope of time in order to test for differential change over time. We will also test EXP vs. ACC differences in follow-up-centered intercepts. A linear model is a reasonable model of social growth for such a short period (i.e., three months) with people who have a social impairment. The random intercept and slope accommodate dependency of time (pre, post, follow-up) within participant. Dependency of participants within cohort will be corrected for using design-robust standard errors (following procedures in Sterba¹²⁶). Site effects are not anticipated but will be examined by including 2 dummy covariates for site as predictors of intercepts and slopes; if not significant, these covariates will be removed. This model will be run in Mplus¹²⁷ general multilevel and structural equation modeling software capable of fitting both the univariate multilevel models for Specific Aim 1 and the multivariate multilevel models for Specific Aim 2, below.

Specific Aim 2: Linking Degree of Target Engagement and Mechanism-Based Functional Outcomes

Hyp 2.2. Growth in memory for faces (NEPSY, ERP) will mediate the effect of treatment on growth in social behavior (SRS, CASS).

Statistical Analysis: To address Hyp 2.2, we will use a multivariate multilevel growth model (involving a linear growth model for memory and another linear growth model for social behavior). We will specify a mediation pathway at the participant-level from treatment (x) to the slope of memory for faces (m) to the slope of social behavior (y). The indirect effect will be tested using the 95% confidence interval around the product of the unstandardized coefficients for the (x→m) and (m→y) paths of the multilevel mediation model following procedures of Lachowicz, Sterba, and Preacher¹²⁸. The confidence interval will be estimated using the Monte-Carlo procedure described in Preacher and Selig,¹²⁹. Exclusion of zero will be interpreted as a significant indirect effect.

Power Using Attrition-adjusted Sample Size: Because missing data will be handled using FIML, the only dropouts will be those with no data (they were randomized but did not show up for any assessment). Past SENSE Theatre studies, including the previous RCT, had less than 10% post-Time 1 attrition. Virginia Tech, in unrelated, recent intervention RCTs had <17% attrition (teens) and 0% (adults); Stony Brook has had 0% attrition in recent RCTs of teens and adults. Thus, to plan conservatively, we will plan for a 90% retention rate. Power analyses were conducted using a proposed sample size that is adjusted for a 10% attrition rate, which is quite feasible. The probability of detecting a treatment effect and the effect size of between-group differences are understandably lower for dependent variables derived from far transfer procedures and for distal variables. The primary dependent variable (memory for faces) and the behavioral measure of social behavior (CASS variable) represent such outcomes. While the estimation of effect sizes from small pilot studies may be limited due to sampling variability¹³⁰, an established literature of theatre-based interventions does not exist. Using past meta-analyses of such outcomes and professional discussion about such effect sizes, clinically important outcomes for treatment-control differences in slopes are those exceeding Cohen's *d* of .25^{131,132}. The guidelines for effect sizes of indirect effects call indirect effects (i.e., product of the standardized coefficients for the x→m and m→y paths) greater than .10 'medium' effect sizes, and such effects are judged to be clinically important¹³³. Regarding Specific Aim 1, we anticipate a Cohen's *d* of at least .5 for the efficacy tests. Regarding Specific Aim 2, based on the past mediation analysis, we expect an indirect effect of at least .23. To demonstrate that our proposed sample size is more than adequate to detect even lower-than-expected effect sizes, we compute the minimally-acceptable effect size for 80% power with 216 participants. For the 2-level multilevel models used in investigating Specific Aim 1, with 216 participants, we will have 82% power for a Cohen's *d* as low as .2 with an ICC for within-participant dependence of .1. For Aim 2, involving mediation effects, we'll need a product of the x→m and m→y standardized coefficients of at least .056 with 216 participants using the confidence interval around the indirect effect to test significance¹³³. There will be plenty of power with the proposed sample size to detect the predicted effect sizes.
